### 8.2 Pre-Operative Evaluation

All subjects will complete the ODI, VAS, and SF-12v2 questionnaires within 90 days prior to the scheduled surgery. All patient questionnaires should be completed during the visit, preferably prior to the patient interacting with the Investigator or other clinical staff. A pertinent medical history will be documented and all subjects will undergo a standard neurological examination including assessments of sensation, motor function, and reflexes.

#### 8.2.1 Pre-Operative Assessment

- Informed Consent
- Inclusion/Exclusion Criteria
- Demographics
- Pertinent History and Physical including Current Symptoms, Height, Weight, and Tobacco Use

- Work/School Status
- Current Medication for Spine Problem
- Neurological Examination
- AP and Lateral X-rays
- Back, Hip/Buttock, and Leg VAS
- Oswestry Disability Index
- SF-12v2
- Patient Symptom Questionnaire
- Adverse Event assessment

### 8.3 Hospitalization/Surgery/Discharge

Subjects will be admitted to the hospital according to the Investigator's standard for non-cervical spine surgery. Prophylactic antibiotics may be administered prior to surgery in accordance with the surgeon's standard of care and anesthesia will be administered per standard operating procedures. The device will be implanted in accordance with methods detailed in the instructions for use for the respective device systems.

Data points required on the Operative case report form must be documented at the time of surgery. Intra-operative adverse events must be recorded.

A Subject may be excluded from the study intra-operatively at the discretion of the Investigator if unexpected findings/occurrences dictate deviation from the intended study procedure. Justification for an intra-operative exclusion and alternative surgical procedure must be fully documented in the subject's medical record and on the Study Exit case report form. A subject who is excluded intra-operatively will be considered an overall treatment failure.

If the patient experienced an adverse event(s) during the hospitalization it should be documented and recorded on an Adverse Event case report form. The subject may be instructed to return to normal activity at the discretion of the Investigator.

Additional post-operative restrictions may be imposed according to the standard of care normally utilized by the Investigator. In addition, subjects should be instructed to notify the Investigator if experiencing untoward events including but not limited to noticeable pain, numbness, tingling, or weakness that does not decrease with rest, swelling of the lower extremities that does not decrease, or increased pain, erythema, edema or drainage from the surgical incision. The Investigator should then determine if an evaluation is warranted.

#### 8.3.1 Surgery/Hospital Discharge Evaluation

- Date of Hospital Admission
- Date of Surgery
- Date of Hospital Discharge
- Implanting Surgeon
- Implanted System Detail
- Surgery Detail/Concomitant Procedures
- Surgery Time (initial incision to closure)
- Anesthesia Time
- Fluoro Time
- Estimated Blood Loss
- Neurological Examination
- Back, Hip/Buttock, and Leg VAS
- Oswestry Disability Index
- SF-12v2

- Patient Symptom Questionnaire
- Adverse Event assessment – Surgery Through Discharge

#### 8.4 Post-Operative Follow-Up Visits

All subjects will be required to return for follow-up visits at initial post-op, 3 months, 6 months, 12 months, and 24 months post-procedure. Data collected at each follow-up visit must be confirmable by source documents and the appropriate case report forms must be completed. All patient questionnaires should be completed during the visit, preferably prior to the patient interacting with the Investigator or other clinical staff. If a site requires multiple follow-up visits within the “initial post-op” timeframe (discharge to 8 weeks post-op), only the latter of the visits will be utilized for data collection. Requirements at each post-operative follow-up visit are as follows:

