## 2 INTRODUCTION

### 2.1 Study Purpose

The purpose of this study is to evaluate the complication rate of the RAVINE Lateral Access System with the ALEUTIAN Lateral Interbody Spacer System or the CASCADIA Lateral Interbody Spacer System compared to the literature reported results with the NuVasive XLIF® system, with particular interest in the incidence of thigh/leg pain and dysesthesia.

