### 5.2 Primary Safety Objectives

The primary safety objectives are:

- The evaluation of all adverse events including device related, procedure related and additional serious adverse events.
- Additional surgical intervention at the operative site including the need for removals, revisions, re-operations or supplemental fixation required to modify the device
- The incidence and severity of any psoas muscle injury, genital femoral nerve injury and lumbar injury will be determined for all patients

All adverse events will be documented on a continuous basis and reviewed by K2M Clinical Research Staff. Information regarding all device failures including instrument breakage, implant breakage, subsidence, migration, or expulsion will be captured.

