#### 5.3.2 Incidence of Thigh Pain/Dysesthesia

A neurological evaluation of the patient, with specific evaluation of psoas muscle weakness, radiating radicular pain, knee extension weakness, dorsiflexion weakness, plantarflexion weakness and anterior thigh numbness will be performed by the healthcare staff and will also be addressed through a patient questionnaire entitled Patient Symptom Questionnaire.

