##### 8.4.1 Follow-Up Evaluations and Data – Post-Op through 24 Months

- Work/School Status (including release for return to work/school) (all visits)
- Current Symptoms (all visits)
- Medication (taken for spine problem since last contact) (all visits)
- Neurological Examination (all visits)
- AP and Lateral X-rays (6 Month, 12 Month, and 24 Month visits)
- Flexion/Extension X-rays (12 Month and 24 Month visits)
- Fusion Assessment (per X-rays and/or CT Scan as determined by the investigator)
- Back, Hip/Buttock, and Leg VAS (all visits)
- Oswestry Disability Index (all visits)
- SF-12v2 (all visits)
- Adverse Event assessment (all visits)
- Patient Symptom Questionnaire (all visits)
- Patient Satisfaction (12 and 24 Month visits only)
- Odom’s Criteria (24 Month visit only)
- Study Exit

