## 9.2 Adverse Event Reporting

Any AE that occurs during the subject's participation in the study will be recorded on the Adverse Event case report form. Pre-existing medical conditions or symptoms occurring prior to the initiation of the study will not be reported as AEs but a worsening of a pre-existing medical condition or symptom will be reported as an AE. Pain, neurological status and functional impairment should be considered AEs when a subject's complaint for any of these symptoms results in an unscheduled visit or when a subject presents with new or worsening symptoms as compared to a previous visit.

All AEs will be followed until the event is resolved or considered to be stable. Relevant source documentation must be available to confirm the occurrence of an AE and must be provided to the sponsor upon request.

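### Keeping only the last visit in the first 8 weeks may understate visit-based thigh pain and dysesthesia, and to a different degree at each site

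*Combined protocol and SAP*

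**What the plan says.** Section 8.4 defines one initial post-operative window, "discharge to 8 weeks post-op", with no target day. If a site requires more than one visit in it, "only the latter of the visits will be utilized for data collection". The sentence leads into the list in section 8.4.1, which covers the neurological examination, current symptoms, the Patient Symptom Questionnaire, VAS, ODI, SF-12v2 and the adverse event assessment. No item is exempted.

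Section 2.1 sets out to compare the complication rate with published XLIF results, "with particular interest in the incidence of thigh/leg pain and dysesthesia". Section 5.3.2, the secondary objective for that incidence, describes a neurological evaluation by staff and says that the topic "will also be addressed through a patient questionnaire entitled Patient Symptom Questionnaire". Section 5.1 adds that every report of pain, numbness or tingling is to be captured and evaluated.

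Other sections provide further routes:

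- Section 8.3.1 puts the same examination and questionnaire at discharge, with an adverse event assessment labelled "Surgery Through Discharge".
- Section 5.2 states: "All adverse events will be documented on a continuous basis and reviewed by K2M Clinical Research Staff".
- Section 9.2 treats pain and neurological status as adverse events "when a subject presents with new or worsening symptoms as compared to a previous visit", or when a complaint leads to an unscheduled visit.
- Section 12.6 plans descriptive adverse event rates at each follow-up interval.

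**The concern.** One record per visit window is ordinary data handling for a score such as VAS or ODI, where the aim is the state at a time point. It suits an incidence less well. A symptom that comes and goes between two early visits is a case, and the retained visit will not show it. Within the visit-based data, discarding an examination can only lower the count of subjects who ever had the symptom.

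Retention also follows site habit. A site with a single 2-week visit contributes week-2 findings. A site with visits at weeks 2 and 6 contributes only week-6 findings. With up to 15 sites and no target day, the initial-visit rate may mix different quantities. Section 12.8 plans a check that sites can be pooled but does not mention visit timing.

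What is at stake is how well the study can describe early thigh symptoms, the complication it singles out.

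**Working it through.** **Step 1: the plan's own figure.** The documents give no number for thigh pain or dysesthesia. The only sizing is for 24-month VAS (section 12.3): true mean improvement 3.66, criterion 3.25, SD 2.0, n = 189, one-sided alpha 0.05.

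- Noncentrality = (3.66 − 3.25) / (2.0/√189) = 0.41 / 0.1455 = 2.82.
- One-sided t-test power = 87.8% (normal approximation 88.0%), which agrees with the stated figure of more than 87%.
- 189 / 0.85 = 222.4, which agrees with 222 enrolled.

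None of these inputs involves the 8-week window, so the rule does not affect them.

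**Step 2: which symptoms can be lost.**

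| Symptom course | Where the plan records it |
|---|---|
| Present at discharge | Discharge examination and questionnaire (8.3.1) |
| Present at the retained early visit | Initial follow-up form (8.4.1) |
| Starts after discharge, gone before the retained visit | Adverse event form, if the site reports it (5.2, 9.2); otherwise nowhere |

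Only the third row is exposed. Section 8.4.1 asks for medication since the last contact but for symptoms only as they currently are, and states no recall period for them. The unscheduled-visit form (8.5) is for visits outside the schedule that the investigator judges related to the device or procedure. A routine 2-week visit that the site itself requires does not clearly qualify.

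**Step 3: illustration, on assumptions only.** Suppose a site sees patients at week 2 and again at week 6 or week 8, and symptom duration is exponential with median m weeks. A subject symptomatic at week 2 is still symptomatic g weeks later with probability 0.5^(g/m).

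| Assumed median m | Still visible at week 6 (g = 4) | Still visible at week 8 (g = 6) |
|---|---|---|
| 2 weeks | 25% | 12.5% |
| 4 weeks | 50% | 35% |
| 12 weeks | 79% | 71% |
| 26 weeks | 90% | 85% |

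The share of week-2 cases not seen at the retained visit is one minus these values. It runs from 10% (1 − 0.90) to 87.5% (1 − 0.125).

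These are upper bounds. If a is the share of those cases that began after discharge and r is the share of the otherwise lost cases recovered through adverse event reports, the net loss is a × (1 − r) × (1 − 0.5^(g/m)). With a = 1 and r = 0 it equals the bound. With a = 0 or r = 1 it is zero. The documents give none of a, r, m, the visit days or the proportion of sites with several early visits, so no point estimate is possible.

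**The case against.** The strongest reply is that the visit form is not the main safety record. Section 9.2 requires any adverse event during participation to be recorded, and new thigh pain at a 2-week visit meets its definition. Subjects are told to report pain, numbness, tingling or weakness that does not decrease with rest (8.3), monitors check adverse event reporting (11.3), and the planned safety output is adverse event rates (12.6). Thigh pain/dysesthesia is a secondary objective, and the extra visits are site practice.

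Much of this stands. It removes any claim that these symptoms are certainly lost. It does not settle the matter. The adverse event assessment is itself on the list that the rule introduces, so a site could read sections 8.4 and 9.2 as conflicting. The adverse event route depends on investigator reporting rather than a structured questionnaire. Section 12.6 names no thigh pain/dysesthesia table, and no section says which source defines that incidence.

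A reader might also infer that the discharge examination comes too early to see approach-related symptoms. The documents do not say so. Section 2.6.2 ties these symptoms to the splitting of the psoas at surgery, and those present at discharge are recorded there.

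**Conclusion.** The point holds in a limited form. At sites with several early visits, the visit-based incidence of thigh pain/dysesthesia that starts after discharge and resolves before the retained visit may be understated, and it may differ between sites by visit schedule. The discharge assessment and adverse event reports recover an unknown part. The illustration allows anything from no loss to most week-2 cases, depending on assumptions the documents cannot settle.

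Two stronger readings are not supported. One is that the trial's complication rate is biased in the device's favour against XLIF. The documents give no published thigh-symptom rate and do not say how the cited papers counted early symptoms, so the direction of that comparison is unknown. The other is that a later retained visit always records fewer cases than a single early one. It can also catch symptoms that begin after week 2, so the difference between sites has no fixed sign.

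The 24-month VAS endpoint and the sample size are untouched. The change is worth making because a stated rule discards data on the outcome of particular interest and is cheap to narrow.

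**What to change.** - In section 8.4, limit the last-visit rule to VAS, ODI and SF-12v2, and state that it never limits adverse event or symptom capture.
- Record the neurological examination and Patient Symptom Questionnaire from every visit in the window.
- At the retained visit, add a question on thigh symptoms since the last contact, so that capture depends less on the number of visits.
- In sections 5.3.2 and 12.6, define early thigh pain/dysesthesia as any occurrence from surgery to 8 weeks, from the examination, questionnaire and adverse event form combined. Report prevalence at the retained visit alongside it.

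The cost is protocol wording, one added question, and somewhat more data entry at visits that already take place. An any-occurrence count gives sites with more early visits more chances to detect a symptom. The added question reduces this but does not remove it, so the number of early visits should be noted when sites are compared. No sample size change follows.

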##### 8.4.1 Follow-Up Evaluations and Data – Post-Op through 24 Months

- Work/School Status (including release for return to work/school) (all visits)
- Current Symptoms (all visits)
- Medication (taken for spine problem since last contact) (all visits)
- Neurological Examination (all visits)
- AP and Lateral X-rays (6 Month, 12 Month, and 24 Month visits)
- Flexion/Extension X-rays (12 Month and 24 Month visits)
- Fusion Assessment (per X-rays and/or CT Scan as determined by the investigator)
- Back, Hip/Buttock, and Leg VAS (all visits)
- Oswestry Disability Index (all visits)
- SF-12v2 (all visits)
- Adverse Event assessment (all visits)
- Patient Symptom Questionnaire (all visits)
- Patient Satisfaction (12 and 24 Month visits only)
- Odom’s Criteria (24 Month visit only)
- Study Exit

#### 8.5 Unscheduled Follow-Up Evaluation

Subjects may return to the clinic at a time point that is not a scheduled follow-up visit. If the Investigator determines that the return visit is related to the study device or procedure, the Unscheduled Visit portion of the Follow-Up case report form should be completed. If a subject requires a device or procedure related re-operation including supplemental fixation, revision and/or device removal as a result of an unscheduled visit, the Sponsor should be notified immediately and an Adverse Event case report form should also be completed. The requirements for an unscheduled visit are as follows:

- Reason for Visit/Current Symptoms/Pertinent history
- X-rays and/or CT Scan, as needed (if done, a minimum of AP/Lateral for all unscheduled visits that are attributable to a spine-related condition)
- Neurological Examination
- AP, Lateral and Flexion/Extension X-rays
- Flexion/Extension X-rays (12 Month and 24 Month visits)
- Back, Hip/Buttock, and Leg VAS
- Oswestry Disability Index
- SF-12v2
- Patient Symptom Questionnaire
- Adverse Event assessment

## 8.6 Schedule of Evaluations

### 8.6.1 Schedule of Evaluations

Interval → Assessment ↓	Pre-Op	Operative/ Discharge	Initial F/U (Discharge to 8 wks post-op)	3 Mo F/U (± 2 wks)	6 Mo F/U (± 1 mo)	12 Mo F/U (± 2 mos)	24 Mo F/U (± 2 mos)	Unscheduled Visit
Informed Consent	X							
Inclusion/Exclusion	X							
Demographics	X							
Pertinent History	X							X
Work Status/ Current Symptoms	X		X	X	X	X	X	X
Medications for Spine Problems	X		X	X	X	X	X	X
Neurological Examination	X	X	X	X	X	X	X	X
AP & Lateral X-rays	X				X	X	X	If needed
Flexion/Extension X-rays						X	X	If needed
ODI	X	X	X	X	X	X	X	X
Back, Hip/Buttock and Leg VAS	X	X	X	X	X	X	X	X
SF-12v2	X	X	X	X	X	X	X	X
Patient Symptom Questionnaire	X	X	X	X	X	X	X	X
Hospitalization and Surgery Data		X						
Adverse Event Assessment	X	X	X	X	X	X	X	X
Patient Satisfaction						X	X	
Odom's Criteria							X	
Study Exit							X	

## 8.7 Pregnancy during Study Participation

If a subject becomes pregnant during the study, the sponsor should be notified as soon as possible. The subject will remain in the study, but during the pregnancy the study follow-up visit(s) will be modified to exclude the X-ray imaging requirements. At follow-up visits after the pregnancy, the required X-rays should again be performed. Information related to the pregnancy and outcome should be maintained by the site and documented by the Sponsor in monitoring reports during periodic visits.

## 8.8 Protocol Deviations

The Protocol must be followed closely, and the Investigators should not deviate from the protocol unless in the opinion of the Investigator a deviation from the protocol is in the best interest of safety for the subject. A deviation from the Protocol should be reported to the sponsor as soon as possible after the deviation is noted. In addition, during routine monitoring visits the monitor may determine a protocol deviation and initiate the protocol deviation process. All protocol deviations must be documented on a Protocol Deviation case report form. For the scientific integrity of the study, protocol deviations must be kept at a minimum. If a site has an unacceptable number of protocol deviations that cannot be explained due to patient safety, the issue will be discussed with the site and corrective action will be considered.

In the event a patient questionnaire is not completed during a visit, permission may be obtained from the sponsor to have that questionnaire mailed into the site within a reasonable amount of time.

## 8.9 Subject Lost to Follow-Up

Every attempt will be made to have all subjects complete the follow-up visit schedule as specified in the protocol. A subject will not be considered lost to follow-up unless efforts to obtain compliance are unsuccessful. If a subject misses a follow-up visit, the site must document attempts to contact the subject by phone twice. If both contact attempts are unsuccessful, a certified letter from the Investigator must be sent to the subject's last known address indicating the subject's commitment to the study and site contact information to arrange a visit. If the subject does not respond, only then will the subject be considered lost to follow-up. If a subject is lost to follow-up, a Study Exit case report form, including a full description of the attempts to locate the subject, must be completed.

## 8.10 Subject Withdrawal

Subjects have the right to withdraw their consent at any time during the study. If a subject requests to withdraw from the study, all information regarding the subject's withdrawal and disposition must be recorded in the subject's medical record. A Study Exit case report form, including a full description of the circumstances related to the withdrawal, must be completed.

## 8.11 Study Case Report Forms

The Sponsor will provide Case Report Forms (CRFs) to the sites for the study, on paper or electronically, as available. Data should be entered with a black ink on the specified locations of the CRFs. On paper CRFs, if an error is made, the incorrect entry should be crossed out with a single horizontal line, the correct entry written next to it, and the correction initialed and dated by the person making the correction. Copies of the CRFs for the study are included as an appendix to the protocol.

### 8.11.1 List of Case Report Forms

- Inclusion/Exclusion
- Pre-Operative
- Operative/Discharge
- Follow-Up Form Covering:
  - Initial Post-Op Follow-Up Visit (discharge to 8 weeks post-op)
  - 3 Month Follow-Up Visit  $\pm$  2 Weeks
  - 6 Month Follow-Up Visit  $\pm$  1 Month
  - 12 Month Follow-Up Visit  $\pm$  2 Months
  - 24 Month Follow-Up Visit  $\pm$  2 Months
  - Unscheduled Visit
- Patient Questionnaires
  - Oswestry Disability Index
  - Back, Hip/Buttock and Leg Visual Analog Scale (VAS)
  - SF-12v2
  - Patient Symptom Questionnaire
- Adverse Event
- Protocol Deviation
- Study Exit

## 9 ADVERSE EVENTS

### 9.1 Definitions

#### 9.1.1 Adverse Event

An Adverse Event (AE) is defined as any untoward medical occurrence in a subject undergoing surgery in this trial which does not necessarily have a causal relationship with this intervention. An AE can, therefore, be any unfavorable and unintended sign (including an abnormal laboratory finding), symptom, or disease temporally associated with the use of the one of the devices, whether or not the event is considered causally related to the use of the device. Any worsening of a pre-existing condition or illness is considered an AE. Laboratory abnormalities and changes in vital signs are considered to be AEs only if they result in discontinuation from the study, necessitate therapeutic medical intervention, and/or if the Investigator considers them to be AEs.

#### 9.1.2 Serious Adverse Event

Any AE that results in one or more of the following is considered a Serious Adverse Event (SAE): death, life threatening situation, inpatient hospitalization, persistent or significant disability/incapacity, and other medically important events. Definitions of SAEs are:

**Death**: the subject dies during participation in the study.

**Life threatening situation**: the subject is at risk of death at the time of the event, but does not refer to the hypothetical risk of death if the AE were more severe or were to progress.

**Inpatient hospitalization**: a subject requires hospitalization or prolongation of an existing hospitalization, including medical or surgical intervention to prevent permanent impairment to a body structure or body function during participation in a clinical study.

**Persistent or significant disability/incapacity**: any AE having an outcome that is associated with a substantial disruption of the ability to carry out normal life functions. This includes the inability to work, but is not intended to include transient interruptions of daily activities.

**Other medically important events**: important medical events that may not result in death, be life-threatening, or require hospitalization (including emergency room visits) but may be considered a serious AE when, based upon medical judgment, they may jeopardize the subject.

Reports of all Serious Adverse Events, as classified by the Investigator, will be reviewed on a periodic basis by the Medical Monitor.

